## **8. SELECTION AND WITHDRAWAL OF SUBJECTS**

### **8.1. Informed Consent**

A potential subject may be screened for eligibility only after the nature of the study, its purpose, and any other information relevant to the subject's decision to participate have been explained to him or her and the subject has voluntarily confirmed his or her willingness to participate. Informed consent is documented by means of a written, signed, and dated informed consent form (ICF). Additional information is provided in [Section 15.4](#).

### **8.2. Subject Inclusion Criteria**

Subjects who meet the following criteria will be considered eligible to participate in the clinical study:

#### **Inclusion Criteria:**

1. Male or female subjects aged 18 - 65 years of age, inclusive, in good general health as determined by medical evaluation (medical history, physical examination, vital signs, 12-lead electrocardiogram [ECG] and clinical laboratory evaluations).
2. Females who are not of childbearing potential (defined as at least 12 months natural spontaneous amenorrhea, or at least six weeks following surgical menopause) or females of childbearing potential who agree to comply with the contraceptive requirements of the protocol.
3. Subject is willing and able to provide written informed consent prior to performing study procedures and be able to read and understand the study protocol.
4. Subject understands and agrees to comply with all planned study procedures.
5. Subject's right and left forearms must be free of large tattoos or skin abnormalities that would interfere with skin test administration and assessment in the opinion of the Investigator.
6. **For healthy uninfected subjects (Cohort 1):** Must have no history of signs or symptoms consistent with SARS-CoV-2 infection at any time within six months of enrollment AND in the Investigator's opinion, have no known intimate exposure or close contact to persons confirmed positive for SARS-CoV-2 infection.
7. **For recovered subjects (Cohort 2):** Must be > two months removed from confirmed diagnosis of SARS-CoV-2 infection independent of vaccination status.

8. **For subjects who have received a SARS-CoV-2 vaccine (Cohort 3):** must have received their final vaccination or booster dose at least four weeks prior to enrolment into the study with no known history of natural infection.
9. Subject receives a **negative SARS-CoV-2 PCR** test result at their screening or baseline visit.

### **8.3. Subject Exclusion Criteria**

Subjects who meet one or more of the following criteria will not be considered eligible to participate in the clinical study:

#### **Exclusion Criteria:**

1. Female subjects who are pregnant or breastfeeding or planning to breastfeed at any time through 90 days after the Screening Visit.
2. Diagnosed with clinically significant and currently relevant cardiac disease:
  - Significant arrhythmia; heart block; heart failure; symptomatic coronary artery disease), recent myocardial infarction [within the past 2 years]) or QTcF >450 msec (male) or >470 msec (female).
3. Presence of erythema nodosum, eczema, psoriasis, or cellulitis.
4. Treatment with systemic corticosteroids, immunosuppressive drugs or any anti-viral treatment within two weeks prior to Screening.
5. History of immunosuppressive disease.
6. Prior adverse reaction to phlebotomy.
7. Prior adverse reaction to CANDIN® or similar material.
8. History of hypersensitivity to the study materials used for phlebotomy (i.e., latex, rubbing alcohol, cotton swabs, bandaids).
9. Documented allergic reaction to any of the excipients contained in the IP (e.g., polysorbate).
10. Subjects with dermatographism.
11. Subjects will be excluded if they have clinically significant underlying conditions associated with high risk for severe COVID-19 infections as identified by the Centers for Disease Control and Prevention (CDC) ([Appendix 2](#)). These conditions include, but are not limited to: chronic obstructive pulmonary disease, diabetes mellitus (Type 1 and 2), obesity, hypertension, heart disease, and cerebrovascular disease.

- Investigators should contact the Medical Monitor with questions regarding clinical significance of underlying conditions.
- 12. The subject has any clinically significant, uncontrolled, or unstable medical or surgical condition that could affect his or her ability to participate in the study or potentially compromise his or her well-being during the study.
- 13. Unable to understand the protocol requirements, instructions and study related restrictions, the nature, scope and possible consequences of the clinical study.
- 14. Healthy uninfected subjects who have any history of SARS-CoV-2 infection by clinical history or laboratory diagnosis (**Cohort 1 only**).

## 8.4.        Restrictions

### 8.4.1.      Medication

Medication restrictions applicable before dosing are described in [Section 8.3](#) (exclusion criteria). Prior medication will be recorded.

Any medicinal product, prescribed or over-the-counter, taken by a subject other than the IPs, is considered concomitant medication. Any concomitant treatment will be given only if deemed strictly necessary by the Investigator or designee. Use of concomitant medication will be recorded and reported.

Subjects will be asked to report any vaccinations and/or boosters from time of study entry (signing of informed consent) until after study exit (early termination or completion of Visit 7, Day 180).

### 8.4.2.      Contraception Rules

Female subjects are allowed to participate in the study if they are:

- a) **Not of childbearing potential** defined as: post-menopausal (defined as at least 12 months natural spontaneous amenorrhea, or at least 6 weeks following surgical menopause), *or*
- b) Naturally or surgically sterile (hysterectomy; bilateral oophorectomy; bilateral tubal ligation with surgery at least six weeks prior to study initiation).
- c) Non-pregnant, non-lactating with negative pregnancy test at the Screening Visit and who use at least one of the following effective contraception options:
  - i. Stable hormonal contraceptive for  $\geq 90$  days prior to screening and for at least seven days after final dose. If  $< 90$  days prior to the study, additional use of one other effective contraception method until 90 days are reached is required, *or*

- ii. Placement of an intrauterine device or intrauterine hormone-releasing system, or
- iii. Use of double barrier methods of contraception (eg, male condom with diaphragm, male condom with cervical cap), or
- iv. Successful male sterilization of the sole partner (subject must verbally confirm that appropriate post-vasectomy documentation of the absence of sperm in the ejaculate was provided after the procedure), or
- v. True abstinence, when in line with the preferred and usual lifestyle of the subject.

**Note:** *Periodic abstinence, such as calendar, ovulation, symptothermal, post-ovulation methods, and withdrawal are not acceptable methods of contraception.*

## **8.5. Randomization Criteria**

Not applicable as this will be an open-label study.

## **8.6. Subject Withdrawal Criteria**

Subjects may withdraw from the study at any time at their own request without stating the reason(s) for withdrawal. A subject must be withdrawn by the Investigator (or by the Sponsor via the Investigator) from the study if one or more of the following occur:

- Withdrawal of consent by the subject.
- Withdrawal of subject by the Investigator or designee if inter-current illnesses occur that may invalidate the study data, if the subject was enrolled in violation of the study protocol, or if a significant study protocol violation occurred, at the discretion of the Investigator or designee.
- If discovered that the subject has entered the study in violation of the inclusion/exclusion criteria stated in the protocol.
- Critical protocol violation occurs during the study.
- Pregnancy during the treatment period.
- Lost to follow-up (i.e., following at least two telephone contact attempts and 1 certified letter).
- Investigator or the Sponsor stops the study, for any reason (e.g., suspension or discontinuation of study drug development).
- Investigator, medical monitor and/or Sponsor decision for any other reason not listed above that may jeopardise the health and/or safety of a subject or invalidate the results of the study.

A genuine effort must be made to determine the reason(s) why a subject fails to return for the necessary visits or is discontinued from the study. If the subject is unreachable by telephone, a registered letter, at the minimum, should be sent to the subject requesting him/her to contact the clinical unit.

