### **8.6.1 Study Halting and Study Stopping Rules**

Dosing may be halted temporarily to investigate before the entire study is terminated. If any of the below events occur, enrollment and dosing should be halted study-wide pending review by the Sponsor, Investigator, and/or Medical Monitor. Subjects enrolled in the study must continue to be followed for the duration of the study.

- One or more subjects with a serious adverse event (SAE) considered definitely, probably, or possibly related to the IPs.
- Three or more subjects with the same or similar grade 3 or higher AEs of the same type considered definitely, probably, or possibly related to IPs.
- One AESI, considered at least possibly related to the IPs.

If any of these events occur, enrollment and dosing should be paused study-wide pending review by the Sponsor, Investigator, and/or Medical Monitor. Subjects enrolled in the study must continue to be followed for the duration of the study.

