#### **12.1.10. Skin test results assessment**

Investigational products are administered in two stages at Visit 1, as described in [Section 10.4](#). In Stage 1 administration, subjects will receive the diluent (negative control), followed by the “1:10 dilution” strength of TNX-2110, TNX-2120, TNX-2130 in their left forearm, and CANDIN®

(positive control) in their right forearm. In Stage 2 administrations, subjects will receive the “undiluted” dose strength of TNX-2110, TNX-2120, TNX 2130 in the right forearm. The order and specific locations of injections are indicated in Table 4 and the Pharmacy Manual ([Appendix 5](#)). A ballpoint pen will be used to mark the arm but also describe precise location of injections (i.e., start three inches from antecubital crease).

The area of induration will be measured at injection sites on the volar aspect of each forearm ([Figure 2](#)). To ensure standardization, calipers will be used to ensure accurate measurement of induration. A member of the study team will visually inspect injection site under good light and measure the induration (thickening of the skin), not erythema (reddening of the skin). Measurements will be made across two diameters. The mean of the longest and midpoint orthogonal diameters of the indurated area should be reported as the DTH response. For example, a reaction that is 10 mm (longest diameter) by 8 mm (orthogonal diameter) has a sum of 18 mm and a mean of 9 mm. The DTH response is therefore 9 mm. The diluent (negative control) is expected to elicit a negative skin test result (i.e., <5 mm), and the CANDIN (positive control) is expected to elicit a positive skin test result (i.e.,  $\geq 5$  mm).

A digital caliper will be used to measure the area of induration as shown in above diagram. All the information (e.g., date and time of test administration, injection site location, lot number of peptide and measurement of area of induration) will be recorded in the CRF.

Further details regarding skin test administration and measurement are provided in the Pharmacy Manual ([Appendix 5](#)).

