7.1.4. Handling of Dropouts or Missing Data

Any subject who withdraws from the study will not be replaced.

Unless specified otherwise in any of the previous sections, missing data will not be imputed.

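### Section 8.6 takes injected subjects out of the study, and so out of safety follow-up to Day 180, if they are found ineligible or have a critical violation

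*Protocol*

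**What the plan says.** Protocol 8.6 states that "A subject must be withdrawn by the Investigator (or by the Sponsor via the Investigator) from the study" when any of a list of events occurs. Three bullets matter here:

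- The second covers enrolment in violation of the protocol, and acts "if a significant study protocol violation occurred, at the discretion of the Investigator or designee".
- The third has no such qualifier: "If discovered that the subject has entered the study in violation of the inclusion/exclusion criteria stated in the protocol".
- The fourth reads "Critical protocol violation occurs during the study".

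None of them distinguishes a subject who has been injected from one who has not.

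On dosing, Protocol 12.1.10 says "Investigational products are administered in two stages at Visit 1", with a 60-minute observation period between the stages (Protocol 10.4). After that come skin readings at 48, 72 and 96 hours and safety contacts up to the Day 180 telephone visit.

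On analysis, the Safety Population holds everyone given one or more IP injections, whether eligible or not (Protocol 13.1, SAP 6). SAP 7.1.4 does not impute missing data in general and adds: "Any subject who withdraws from the study will not be replaced".

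**The concern.** The rule joins two different acts: giving no more product, and collecting no more data. In this trial exposure is over within hours and observation runs for about six months. For a fully dosed subject, the only remaining effect of withdrawal is on data collection.

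Safety is one of the two primary objectives. Under SAP 2.3 and 10 it is also the only outcome still to be assessed. One of the two adverse events of special interest is enhanced disease on repeated exposure to the virus, and new COVID-19 infection is asked about at the Day 30 and Day 180 calls. Those two contacts are lost for any subject withdrawn in the first days. That subject still counts in the denominator, so the tables would not show that the later period went unobserved.

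**Working it through.** The plan gives no figure to reproduce: there is no sample-size calculation and no expected withdrawal rate. The check compares sections and then gauges the size.

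**Can ineligibility come to light after dosing?** Yes. Inclusion criterion 1 (Protocol 8.2) relies partly on clinical laboratory evaluations. Table 3 and Protocol 12.2.2 place that blood draw at Visit 1, just before Stage 1, and Protocol 16.6 sends samples to a central laboratory. Only the PCR result is required to be negative before phlebotomy and injection (Protocol 12.1.7).

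**Does another section keep the subject in follow-up?** Continued follow-up is stated for a study-wide halt (Protocol 8.6.1) and for pregnancy after discontinuation (Protocol 14.4). Deaths reported after participation must be notified (Protocol 14.3.1). Protocol 5.4 speaks of following adverse events to resolution, which covers events already present but not new ones. Nothing covers new non-fatal events in a subject withdrawn under the third or fourth bullet.

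**Is withdrawal needed to protect the efficacy sets?** Not for ineligibility. ITT requires that all entry criteria be met, and mITT is drawn from ITT. Neither has a criterion for critical violations during the study.

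**How are the percentages formed?** SAP 4.1 generally divides by the total in the analysis population and uses non-missing counts only for by-visit displays. The adverse-event summaries in SAP 9.1 are not by visit, so a withdrawn subject stays in the denominator.

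**Size for one subject.** Withdrawal after the Day 5 reading loses 180 − 5 = 175 days, or 175/180 = 97% of planned follow-up. Withdrawal on Day 1 loses 179.

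**Size for the trial.** Inputs: n = 90 planned (SAP 3.2); w = number injected and then withdrawn before the late period, assumed to be 0, 5 or 10.

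- Upper limit with zero late events, one-sided 95%: U = 1 − 0.05^(1/(90 − w)).
- Chance of seeing at least one late event at an illustrative true rate of 2%: 1 − 0.98^(90 − w).
- Expected reported late percentage as a share of the true one, if withdrawn subjects have the same risk as the rest: (90 − w)/90.

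| w (assumed) | Followed late | U | P(at least 1) at 2% | Reported/true |
|---|---|---|---|---|
| 0 | 90 | 3.27% | 83.8% | 100% |
| 5 | 85 | 3.46% | 82.0% | 94.4% |
| 10 | 80 | 3.68% | 80.1% | 88.9% |

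For one cohort of 30, U is 9.50% with complete follow-up and 10.50% if 3 are withdrawn (27 followed).

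**Internal conflict.** A subject enrolled against the eligibility criteria falls under both the second bullet, where withdrawal is discretionary, and the third, where it is compulsory. Both sit under the same compulsory opening sentence.

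**The case against.** The best reply is that 8.6 is narrower, and the loss smaller, than it looks. Much of that stands, and several stronger readings should be set aside.

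- A reader might infer that any protocol violation forces withdrawal. The text does not say so: only a critical violation does, and a significant one is left to the Investigator.
- A reader might infer that withdrawal never prevents exposure. That is true only after Stage 2. Protocol 13.4 counts a subject as enrolled on signing consent, so ineligibility found before Stage 1 would prevent every injection, and in the 60-minute gap the second set.
- A reader might infer that 8.6.1 contradicts 8.6, because it says "Subjects enrolled in the study must continue to be followed for the duration of the study". It governs a study-wide pause, not an individual's withdrawal. It shows that the protocol can separate dosing from follow-up, but it is not a contradiction.
- A reader might infer that ineligible subjects are at higher risk, so that the bias is large. No passage supports this. Several entry criteria concern cohort history, vaccination timing or the condition of the forearms.
- A reader might infer that the subject's whole safety record is lost. Everything recorded before withdrawal stays in the Safety Population, and later deaths remain reportable.

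What the reply does not supply is a sentence that keeps a fully dosed subject in adverse-event follow-up. A site that follows 8.6 as written would stop it.

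**Conclusion.** The point holds for subjects who have completed Stage 2. For them, compulsory withdrawal for ineligibility or a critical violation prevents no exposure, ends planned safety observation, and leaves the subject in the denominator, so late percentages can be understated. The numerical effect is modest: at 10 withdrawals of 90 the zero-event upper limit rises by about 0.4 percentage points (3.27% to 3.68%). This rests on an assumed number of withdrawals and on the loss of all late follow-up in those subjects. The reported-to-true ratio also assumes equal risk. The direction of any additional selective bias cannot be stated from the documents. The conflict between the second and third bullets is textual and needs no assumption. The change is worth making because safety is a primary objective and the remedy is cheap.

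**What to change.** In Protocol 8.6:

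1. Separate discontinuing further injections from withdrawing from the study. Protocol 13.4 already reports the two separately. Word this so that no rule on whether Stage 2 is given changes; limiting withdrawal to the time before the first injection, without this separation, could be read as permitting Stage 2 in a subject found ineligible during the gap.
2. State that every subject given any injection stays in the scheduled safety follow-up through Visit 7 unless consent is withdrawn, and that the deviation is recorded.
3. Handle ineligibility through ITT and mITT, which already exclude it, and flag critical violations in the deviation listing of SAP 8.2, since neither population definition covers them.
4. Reconcile the second, third and fourth bullets on what is discretionary and what is compulsory.

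If follow-up is already complete, report how many injected subjects were withdrawn under these bullets and how long each was observed.

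The cost is a short protocol amendment with IRB review, and renewed consent if the consent form is revised. The contacts themselves (Visits 2 to 5 and the two later calls) are already scheduled.

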### **8.6.1 Study Halting and Study Stopping Rules**

Dosing may be halted temporarily to investigate before the entire study is terminated. If any of the below events occur, enrollment and dosing should be halted study-wide pending review by the Sponsor, Investigator, and/or Medical Monitor. Subjects enrolled in the study must continue to be followed for the duration of the study.

- One or more subjects with a serious adverse event (SAE) considered definitely, probably, or possibly related to the IPs.
- Three or more subjects with the same or similar grade 3 or higher AEs of the same type considered definitely, probably, or possibly related to IPs.
- One AESI, considered at least possibly related to the IPs.

If any of these events occur, enrollment and dosing should be paused study-wide pending review by the Sponsor, Investigator, and/or Medical Monitor. Subjects enrolled in the study must continue to be followed for the duration of the study.

## **9. TREATMENT OF SUBJECTS**

### **9.1. Prior and Concomitant Medications**

All prescription and over-the-counter medications used in the last three months before screening should be recorded at each visit (scheduled or unscheduled) in the case report form (CRF).

The use of corticosteroids, immunosuppressive drugs or any anti-viral treatment within two weeks prior to Screening is prohibited (see [Section 8.3](#)).

## 10. INVESTIGATIONAL PRODUCT

### 10.1. Identity of the Investigational Products

TNX-2100 skin test comprises of three distinct IPs named TNX-2110, TNX-2120 and TNX-2130 examined in this proposed POC study. These IPs fall into three distinct groupings based on the source:

- TNX-2110 – consists of 37 individual peptides which are representative of the dominant SARS-CoV T cell epitopes ([Grifoni et al., 2020](#)).
- TNX-2120 – consists of 98 individual peptides of approximately 20-mer with an approximate overlap of 10 amino acids. These peptides represent 1273 AA in SARS-CoV-2 spike ([NCBI Reference Sequence: YP\\_009724390.1](#)).
- TNX-2130 – consists of 16 individual peptides of approximately 20-mer with an approximate overlap of 10 amino acids. These peptides represent Orf3b (57 residue variant: [Chan et al., 2020b](#); 57 and 22 residue variants: [Konno et al., 2020](#)) and Orf8 ([Chan et al., 2020b](#))

Each IP contains 2.5 µg / mL per each peptide per vial (2 mL total volume per vial) in addition to compendial excipients. The IPs are provided as frozen liquid formulations containing phosphate buffer pH 7.0 with 0.31% polysorbate 20 and 4.6% mannitol. All IPs need to be thawed prior to use.

In addition, a “Diluent” is provided for a further manual dilution of the IPs. TNX-2100 “Diluent” is provided as a sterile solution consisting of phosphate buffer pH 7.0 with 0.31% polysorbate 20 and 4.6% mannitol.

All IPs will be manufactured under current Good Manufacturing Practices as sterile solutions for injection. All excipients are compendial. Refer to the current Investigational Brochure for composition details.

### 10.2. Study Drug Packaging, Labeling, and Storage

IPs will be packaged and labeled according to applicable local and regulatory requirements.

All supplies of IPs must be stored in accordance with the manufacturer’s instructions.

The IPs will be stored in a securely locked area, accessible to authorized persons only, until needed for dosing.

All IPs shall be stored under the following conditions:

1. Long term storage. IP should remain frozen -80°C +/- 10°C until ready to thaw on the day of Visit 1 (Day 1). Thawed IP must not be re-frozen.
2. After material is thawed (approximately 2-3 hours at ambient temperature) IP should be stored at 2 - 8°C until ready to administer. Thawed material should be discarded if not used within 8 hours on the day of thawing. Thawed IP must not be re-frozen.

